The Effectiveness of the Video Conferencing Telerehabilitation Method, Delivered in One on One and Group Sessions, in Urinary Incontinence Cases.

Study Protocol and Statistical Analysis Plan (SAP) (Pages 1 – 21)

November 15,2021

**The Effectiveness of the Video Conferencing
Telerehabilitation Method, Delivered in One on One and Group Sessions, in Urinary
Incontinence Cases.**

Study Protocol (Pages 2-6)

November 15,2021

Study Protocol

Study titled “The Effectiveness of the Video Conferencing Telerehabilitation Method, Delivered in One on One and Group Sessions, in Urinary Incontinence Cases.” was approved by Marmara University Faculty of Medicine Ethical Committee at the meeting on 30.11.2020 with approval number: 1195 (Annex-1).

The legal representatives of the patients who participated in the study will be informed about the aim, duration and the programs to be applied throughout the study. Volunteer Information Form will be signed and approved in accordance with the standards deemed appropriate by the Ethical Committee of Marmara University Faculty of Medicine. The study will be conducted in accordance with the Declaration of Helsinki.

Hypothesis of the Study

H0: With one on one video conference method, exercise training is no superiority of exercise training with group video conferencing method in urinary incontinence.

H1: Exercise training with one on one video conference method is more effective in increasing muscle strength in patients with urinary incontinence.

H2: One on one videoconferencing and exercise training are more effective in reducing the degree of incontinence in patients with urinary incontinence.

H3: Exercise training with one on one videoconferencing method is more effective in increasing the quality of life in patients with urinary incontinence.

H4: Exercise training with one on one videoconferencing method is more effective in increasing patient satisfaction in patients with urinary incontinence.

H5: Exercise training with one on one video conference method is more effective in increasing sexual function in patients with urinary incontinence.

H6: Exercise training with one on one videoconferencing method is more effective in increasing exercise adherence in patients with urinary incontinence.

Randomization of the Study Groups

Individuals with Urinary İncontinence applying to Göztepe [name]. Süleyman Yalçın Şehir Hastanesi will be invited to participate in the study. Individuals who volunteered to participate and whom met the criteria for participation will be randomized with simple random sampling method and will be

divided into two groups. In both groups participants will receive same exercise program and physiotherapist will follow up the exercise program every week by video conference method. While only the physiotherapist and the patient will take part in the one-on-one group, there will be a physiotherapist and 8 patients in the group sessions.

Inclusion Criteria

18-65 aged

BMI 18-30 kg/m²

Being diagnosed with stress incontinence or mixed incontinence (dominantly SUI)

Mild or moderate incontinence (mild SUI; urinary incontinence with coughing, sneezing, laughing, or any strenuous activity. Moderate; urinary incontinence with carrying, pushing, lifting, walking, and any light physical activity)

Exclusion Criteria

Pregnancy

Ongoing vulvovaginitis or urinary tract infection or malignancy

Pelvic floor muscle strength is between 0-1 according to the Modified Oxford Scale,

Previous surgery for SUI

Problems with vision or inability to understand given commands

Conservative therapy in the last 6 months

Allergic reaction to the gel used with the perinometer/probe

Evaluations

Evaluation parameters will be applied at the baseline, at the end of 4-weeks treatment program, at the end of 8 weeks treatment program. Outcome measures and applied evaluations are shown in Table 1.

Table 1. Outcome measures and evaluation methods

Primary Outcome Measures	Evaluation Methods
Muscle Strength	-PERFECT Scheme -Surface Electromyography

Secondary Outcome Measures	Evaluation Methods
Symptom Evaluation	-1 hour pad test -The International Consultation on Incontinence Questionnaire-Short Form - Urogenital Distress Inventory- 6 (UDI-6) - Incontinence Impact Questionnaire-7 (IIQ-7) - Overactive Bladder -Validated 8- Question Awareness Tool (OAB-V8)
Patient Satisfaction	Visual Analog Scale (VAS)
Exercise Adherence	VAS Broome Pelvic Floor Muscle Exercise Self- Efficacy Scale
Sexual Function	Female Sexual Function Scale (FSFI)

Treatment Program

The exercises which given the both groups compose same exercise protocols for 8 week. The exercise protocol includes pelvic floor muscle training, diaphragmatic breathing exercise and core exercise will be given the all participants. The participants in the study will be followed up with video conferencing method by weekly.

Group I (one on one video conferencing group): In this group, exercise follow-up and transition to the next exercise phase will be realized with one-on-one video conference interviews.

Group II (group sessions video conferencing group): In this group, exercise follow-up and transition to the next exercise stage will be realized with group video conference sessions consisting of 8 participants.

The Effectiveness of the Video Conferencing Telerehabilitation Method, Delivered in One on One and Group Sessions, in Urinary Incontinence Cases.

Statistical Analysis Plan (SAP) (Pages 7 –8)

November 15,2021

Statistical Analysis Plan (SAP)

In the analysis of the data to be obtained in the study, the significance will be evaluated at the $p < 0.05$ level with the SPSS 22.0 statistical program at the 90% confidence interval. In the evaluation of variables; If the number of cases is sufficient, its conformity to the normal distribution will be questioned with the Kolmogorov Smirnov test and normal distribution graphs. In the examination of the variables, appropriate statistical tests will be applied depending on the provision of parametric or non-parametric test conditions. Normally distributed variables will be expressed as mean and standard deviation, and non-normally distributed variables will be expressed as numbers and percentages. If the groups fit the normal distribution, the evaluation results at the beginning, 4th week and 8th week will be compared with ANOVA, if the normal distribution is not met, comparisons will be made with Kruskal Wallis and appropriate post-hoc tests. In the correlation analysis, the appropriate Spearman or Pearson correlation analysis methods will be preferred. Chi-square test will be used in the evaluation of binary data.

The Effectiveness of the Video Conferencing Telerehabilitation Method, Delivered in One on One and Group Sessions, in Urinary Incontinence Cases.

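### The two-arm design can compare one-on-one with group video delivery but cannot show that video telerehabilitation works, and the SAP's comparison of visits should not be left to carry that conclusion

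*Combined protocol and SAP*

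**What the plan says.** The title, repeated at the head of the protocol and of the SAP, is "The Effectiveness of the Video Conferencing Telerehabilitation Method, Delivered in One on One and Group Sessions, in Urinary Incontinence Cases".

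The formal question is narrower. Under Hypothesis of the Study, H0 reads "With one on one video conference method, exercise training is no superiority of exercise training with group video conferencing method in urinary incontinence", and H1, on the primary outcome, reads "Exercise training with one on one video conference method is more effective in increasing muscle strength in patients with urinary incontinence". H2 to H6 have the same comparative form for the other outcomes.

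Under Randomization of the Study Groups, eligible volunteers are randomised into two groups, and "In both groups participants will receive same exercise program and physiotherapist will follow up the exercise program every week by video conference method". The arms differ in session format: one patient with the physiotherapist, or a session in which "there will be a physiotherapist and 8 patients in the group sessions". Treatment Program confirms a common 8-week exercise protocol. No untreated, usual-care, face-to-face or exercise-without-video arm is described.

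Evaluations sets the visits at baseline, week 4 and week 8. For normally distributed data the SAP says that "the evaluation results at the beginning, 4th week and 8th week will be compared with ANOVA"; otherwise Kruskal-Wallis with post-hoc tests is used. The significance level is p<0.05.

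**The concern.** The title points to one question, the hypotheses to another, and the SAP's only explicit outcome comparison may answer neither.

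Change from baseline in patients who all receive video telerehabilitation combines any treatment effect with whatever else moves over 8 weeks. That includes the natural course of symptoms, regression to the mean in people who enter while seeking hospital care, and practice on PERFECT and surface EMG, which are repeated at each visit. Without an arm that lacks telerehabilitation these parts cannot be separated.

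At stake is the main conclusion. An analyst who followed the SAP sentence as a comparison of visits could obtain a significant result that does not address H0 to H6. Under the present title it could be taken as evidence that telerehabilitation is effective. The plan has no sentence that rules this out.

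**Working it through.** **No figure to reproduce.** The available text gives no sample size, power, effect size or standard deviation. The check is therefore a reading of the text, followed by an illustration on stated assumptions.

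**Step 1: what randomisation identifies.** Write each arm's mean change to week 8 as the following sums.

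- One-on-one: D + T + F1
- Group: D + T + F2

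D is non-treatment change, T is the effect of the shared programme, and F1 and F2 are the effects of format. The difference between arms is F1 − F2, because D and T cancel. This is the contrast in H0 to H6. Neither arm's own change isolates T, since D always comes with it. The title suggests T plus format; the design estimates only the format difference.

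**Step 2: what the SAP sentence compares.** It lists three visits as the things compared. Post-hoc tests are needed only for a factor with three or more levels, and the trial has three visits but two arms, so visit is the natural factor. Against this, the sentence opens with a condition on the groups being normally distributed, and it names no factor, no paired test and no interaction. A comparison of visits is the most natural reading, not a certain one.

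**Step 3: how a comparison of visits behaves with no treatment effect.** Assumptions, none from the documents: 24 patients per arm, correlation 0.5 between visits, a two-sided 0.05 level, and non-treatment drift of d SD by week 8 (half of it by week 4), equal in both arms. For the paired test the SD of change is √(2(1−0.5)) = 1, so the noncentrality is d × √24: 1.47 at d = 0.3 and 2.45 at d = 0.5, on 23 degrees of freedom. The other rows come from 20,000 simulated trials.

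| Test | d = 0 | d = 0.3 | d = 0.5 |
|---|---|---|---|
| Paired, baseline to week 8, one arm | 5% | 29% | 65% |
| Repeated-measures ANOVA over visits, one arm | 5% | 22% | 55% |
| One-way ANOVA ignoring the pairing, one arm | 0.4% | 4% | 20% |
| Between-arm test on change | 5% | 5% | 5% |

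Kruskal-Wallis, the non-parametric test the SAP names, also ignores the pairing. With correlation 0.7 and a shift of 0.30 SD at both later visits, it rejects in about 3% of trials with 24 patients and 11% with 48. Repeated-measures ANOVA gives 46% and 78% in the same setting.

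Three things follow. With no drift, no test exceeds its level. With drift, the rate runs from below 5% to well above it, depending on the test and on inputs the plan does not give. The randomised contrast stays at 5% throughout.

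**Step 4: even the direction is open.** Excluding Modified Oxford Scale grades 0 to 1 removes low strength readings, so regression from that selection would lower later strength and work against apparent improvement on the primary outcome. Practice would work the other way. For symptoms, entry while seeking care favours later improvement, whereas the restriction to mild or moderate incontinence limits high baseline values.

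**The case against.** The strongest reply is that the trial's question lies in its hypotheses, not its title. H0 to H6 all concern the superiority of one-on-one delivery, the title itself names both formats, and a randomised two-arm trial fits that question. This stands. A reader might infer that the trial lacks a control arm it needs; the documents do not support that, because no hypothesis claims an effect against no treatment.

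Second, the SAP names neither a within-arm test nor a factor. A reader might infer that before-after tests are the planned evidence of effectiveness. That goes further than the text, which does not tie any within-arm result to any hypothesis or say how conclusions will be drawn. What survives is that the visits are what the sentence lists, and that nothing in it supplies the arm contrast.

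Third, any false-positive rate depends on assumed drift, correlation and sample size, and on a test choice the SAP leaves open. With the test it does name for non-normal data, the rate can fall below 5%. This also stands, and it is why no single percentage belongs in the conclusion.

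The reply does not remove the limit on interpretation. Under any of these readings, change over time in two arms that both receive telerehabilitation cannot be attributed to telerehabilitation.

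**Conclusion.** The point holds as a limit on interpretation and a gap in the SAP's wording. The design supports the one-on-one versus group comparison in H0 to H6 and does not support a claim that video telerehabilitation is effective. The SAP sentence, most naturally read as comparing visits at p<0.05, does not name the arm or group-by-time term that the hypotheses need, and nothing in the plan keeps a visit effect from being used as the result.

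The size cannot be quantified from the documents. The table shows only that the answer depends on drift, sample size and test. A reader might infer from it that the trial has a known inflated error rate, or that its primary strength outcome is biased towards improvement. Neither follows: inflation requires some non-treatment change, and for strength the entry criteria could push regression the other way.

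The conclusion rests on two premises: that no further control arm appears elsewhere in the plan, and that the SAP sentence compares visits. If an arm or interaction term was meant, stating it would close the analysis gap, while the limit on the title's claim would remain.

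**What to change.** In the SAP:

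- Base conclusions on the randomised difference between one-on-one and group delivery in change from baseline to weeks 4 and 8.
- Report change within each arm as a mean change with a 95% confidence interval, labelled descriptive and without significance tests. The SAP's current 90% level would need to change for this, since 90% corresponds to a two-sided 0.10.
- Add a sentence such as: Within-arm changes are uncontrolled and will not be used to conclude that telerehabilitation is effective; conclusions rest on the randomised difference between the two formats.

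In the protocol, word the aim, and ideally the title, as a comparison of one-on-one with group video delivery, in line with H0 to H6.

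The changes are to wording and analysis only, with no added patients, visits or arms. The downside is that the trial gives up an effectiveness claim that its design cannot support.

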Annex 7. Assessment of Patient Satisfaction

1) How satisfied were you with the treatment you received?

05.....10
(Not satisfied at all) (Very satisfied)

2) How satisfied were you with the decrease in your complaints after your treatment?

05.....10
(Not satisfied at all) (Very satisfied)

3) How satisfied were you that your exercise program is followed by online interviews?

05.....10
(Not satisfied at all) (Very satisfied)

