Annex 8. Assessment of Exercise Adherence

- Visual Analog Scale

How long did you adhere to the exercise program during your treatment?

05.....10

(Not satisfied at all)

(Very satisfied)

- Broome Pelvic Muscle Exercise Self Efficacy Scale

Question	Level of Confidence
Part A: How confident are you that you can:	
1. Contract your pelvic muscles?	0 10 20 30 40 50 60 70 80 90 100
2. Perform pelvic muscle contractions three times a day?	0 10 20 30 40 50 60 70 80 90 100
3. Perform pelvic muscle contractions while lying down?	0 10 20 30 40 50 60 70 80 90 100
4. Perform pelvic muscle contractions while standing?	0 10 20 30 40 50 60 70 80 90 100
5. Perform pelvic muscle contractions while sitting?	0 10 20 30 40 50 60 70 80 90 100
6. Contract your pelvic muscles without contracting your abdominal muscles?	0 10 20 30 40 50 60 70 80 90 100
7. Contract your pelvic muscles while washing fruits under running water?	0 10 20 30 40 50 60 70 80 90 100
8. Contract your pelvic muscles when lifting a bag of groceries?	0 10 20 30 40 50 60 70 80 90 100
9. Contract your pelvic muscles while standing at the sink brushing your teeth?	0 10 20 30 40 50 60 70 80 90 100
10. Contract your pelvic muscles rapidly?	0 10 20 30 40 50 60 70 80 90 100
11. Perform pelvic muscle contractions when you are sad?	0 10 20 30 40 50 60 70 80 90 100
12. Contract your pelvic muscles while showering after a busy and tiring day?	0 10 20 30 40 50 60 70 80 90 100
13. Perform pelvic muscle contractions when you are tired?	0 10 20 30 40 50 60 70 80 90 100
14. Contract your pelvic muscles when you awaken at night with a strong urge to urinate?	0 10 20 30 40 50 60 70 80 90 100
Part B: How confident are you that pelvic muscle contractions will prevent unwanted urine loss:	
1. When you experience a strong urge to urinate?	0 10 20 30 40 50 60 70 80 90 100
2. When you sneeze?	0 10 20 30 40 50 60 70 80 90 100
3. When you laugh?	0 10 20 30 40 50 60 70 80 90 100
4. While waiting 2 minutes for a restroom?	0 10 20 30 40 50 60 70 80 90 100
5. While waiting 5 minutes for a restroom?	0 10 20 30 40 50 60 70 80 90 100
6. When you wake up at night with a strong urge to urinate?	0 10 20 30 40 50 60 70 80 90 100
7. When you lift a heavy package?	0 10 20 30 40 50 60 70 80 90 100
8. When you cough?	0 10 20 30 40 50 60 70 80 90 100
9. When washing fruits and vegetables?	0 10 20 30 40 50 60 70 80 90 100

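### The satisfaction and adherence VAS items have no valid baseline, so any comparison over time or change score that includes baseline is meaningless for H4 and the VAS part of H6; a comparison between arms after treatment is still possible

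*Combined protocol and SAP*

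**What the plan says.** The Evaluations section gives one schedule for everything: "Evaluation parameters will be applied at the baseline", and again after 4 and 8 weeks of treatment. It then points to Table 1, which lists a VAS for patient satisfaction and, for exercise adherence, "VAS Broome Pelvic Floor Muscle Exercise Self- Efficacy Scale". No instrument is exempted from the baseline visit.

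The items themselves are in the annexes:

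- Annex 7, item 1: "How satisfied were you with the treatment you received".
- Annex 7, item 2: "How satisfied were you with the decrease in your complaints after your treatment".
- Annex 7, item 3 asks how satisfied the patient was with the online follow-up of her exercise programme.
- Annex 8, VAS: "How long did you adhere to the exercise program during your treatment".

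The SAP says that, if the data are normal, "the evaluation results at the beginning, 4th week and 8th week will be compared with ANOVA", with Kruskal-Wallis and post-hoc tests otherwise. It makes no exception by outcome. H4 and H6 claim that one-on-one sessions do more than group sessions to increase satisfaction and adherence.

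**The concern.** All four VAS items look back on treatment. At baseline nothing has been received, no complaint has decreased because of it, and there has been no programme to adhere to. The scale is a line from 0 to 10 with no option for not applicable, so a baseline entry would be blank, a placeholder, or a guess.

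The stated schedule and the stated three-time comparison nevertheless both include that entry, and describing the effect in H4 and H6 as an increase invites a change from baseline. Two things are at stake. A rise from an undefined starting point could be reported as a treatment effect. And the question these hypotheses do ask, whether one-on-one delivery gives higher satisfaction and adherence than group delivery, has no named time point or test. H4 is the more exposed, because the VAS is its only instrument.

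**Working it through.** The documents as read give no sample size, SD, or effect size for these outcomes, so there is no figure of the plan's to reproduce. The main check sets the texts side by side. The arithmetic after it is illustration on assumed inputs.

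**1. Can each item be answered at baseline?**

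| Item | What it presupposes | Baseline meaningful? |
|---|---|---|
| Annex 7, item 1 | Treatment received | No |
| Annex 7, item 2 | Complaints reduced after treatment | No (and the wording does not fit week 4) |
| Annex 7, item 3 | Online follow-up has taken place | No |
| Annex 8, adherence VAS | A treatment period | No |
| Annex 8, Broome scale | Present confidence | Yes |

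Recent earlier treatment does not supply a meaning, because conservative therapy within 6 months and previous surgery for stress incontinence are exclusions. The Broome part of H6 is unaffected.

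**2. What does a three-time comparison show if a baseline is recorded anyway?**

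Assumptions: 16, 24 or 32 patients per arm; no difference between arms; mean 7 and SD 2 at weeks 4 and 8 (correlation 0.5), truncated to 0–10; 2,000 simulated trials; both arms pooled for the time comparison; the three visits entered as three groups in a Kruskal-Wallis test. The last column is a t-test between arms.

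| Per arm | Baseline all 0: time test p < 0.05 | Arbitrary baseline (mean 5, SD 2): time test p < 0.05 | Between arms at week 8: p < 0.05 |
|---|---|---|---|
| 16 | 100% | 96.8% | 5.1% |
| 24 | 100% | 99.7% | 4.4% |
| 32 | 100% | 100% | 5.2% |

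The time test responds only to the invented baseline. The comparison between arms behaves as it should.

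**3. What if a change score were used?**

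The plan does not state one; this shows the cost if it were adopted. With the same SD at both visits and correlation ρ, Var(change) = 2·SD²·(1 − ρ). The standard error relative to a week-8 comparison is √(2(1 − ρ)), and the patients needed for equal precision scale with its square.

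- ρ = 0: √2 = 1.41, factor 2.0.
- ρ = 0.25: √1.5 = 1.22, factor 1.5.
- ρ = 0.5: √1 = 1.00, no loss; above 0.5 the ratio is below 1.
- A constant placeholder has no variance, so the ratio is 1.00.

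In terms of power, take an assumed arm difference of 1.5, SD 2, two-sided 0.05, and power ≈ Φ(1.5 / (SD·√(2/n)) − 1.96). For the change score with ρ = 0, SD becomes 2√2.

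| Per arm | Week 8 only | Change from uncorrelated baseline |
|---|---|---|
| 16 | 0.56 | 0.32 |
| 24 | 0.74 | 0.45 |
| 32 | 0.85 | 0.56 |

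**The case against.** The strongest reply is that this is a drafting slip with limited harm. Table 1 has no column for visits, the baseline requirement comes from one general sentence, and the items are so clearly retrospective that staff may well not give them before treatment. These are secondary outcomes. That is fair and limits the severity, but the text as it stands still schedules the entry and includes it in the comparison.

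A reader might go further and infer three things that the documents do not support.

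- *That H4 and part of H6 cannot be tested.* Both are contrasts between randomised arms, and the arms can be compared at week 8 without a baseline. The SAP sentence begins with a condition on the groups, so it can be read as comparing arms at each visit. On that reading the week 8 comparison stands, as does week 4 where the item wording fits, and only the baseline comparison is empty.
- *That the plan allows no other test.* The SAP also promises tests chosen according to whether parametric conditions hold. This is vague, but it does not exclude a week 8 test between arms.
- *That twice the patients are needed.* That figure applies only to a change score, with a varying baseline actually recorded, equal SDs, and correlation near 0.

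If the SAP sentence instead means comparison over time only, the missing contrast between arms affects the other outcomes too, including muscle strength. That is a separate issue, and this point does not rest on it. The invalid baseline would remain after that repair.

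**Conclusion.** The point holds in this form: four VAS items are scheduled and compared at a visit where they have no meaning, so no time comparison or change score that includes baseline can inform H4 or the VAS part of H6. This follows from the wording alone and needs no numerical assumption. It does rest on there being no exception in the pages between the SAP and Annex 2, which were not available; the text that could be read contains none.

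The size depends on how the sponsor proceeds. If the visits are compared over time, a spurious time effect is close to certain under the assumed values (97 to 100%). If a change score is used, the loss ranges from none (ρ = 0.5, or a constant baseline) to a doubling of the sample for equal precision (ρ = 0). If the arms are compared at week 8, there is no loss. The plan should be corrected, although only secondary outcomes are involved.

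A related fault needs correcting at the same time. The adherence VAS asks about duration of adherence, but its end points describe satisfaction, so its score is unclear at any visit.

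**What to change.** - **Evaluations:** state that Annex 7 and the Annex 8 adherence VAS are collected only after treatment starts: at week 8, with week 4 as supportive for items whose wording fits mid-treatment. Annex 7 item 2 does not fit as worded.
- **SAP:** state that H4 and the VAS part of H6 are tested by comparing the two arms at week 8 (t-test or Mann-Whitney), with no change from baseline. Name in advance which satisfaction item, or which composite of the three, decides H4. Any allowance for treatment in groups of 8 should follow whatever is decided for the other outcomes.
- **Hypotheses:** in H4 and the VAS part of H6, replace the language of increase with higher values at week 8 in the one-on-one arm.
- **Annex 8:** replace the satisfaction anchors on the adherence VAS with anchors that describe adherence.
- **Broome scale:** keep its baseline and use it as a covariate when the arms are compared.

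The cost is a few sentences in the protocol and SAP, two corrected anchors, and fewer items to complete at baseline. No patients, visits, or procedures are added.

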Annex 3. Assessment of Muscle Strength

PERFECT SCHEME					
	Power (P)	Endurance (E)	Repetitions (R)	Fast Contraction (F)	Every Contraction Time (ECT)
1					
2					
3					
MEAN					

Surface EMG			
	Resting tone	Maximum Voluntary Contraction (MVC)	Pelvic Floor Muscle Endurance
1			
2			
3			
Mean			

Annex 4. International Consultation on Incontinence Questionnaire-Urinary Incontinence Short Form

Initial number

ICIQ-UI Short Form

CONFIDENTIAL

DAY MONTH YEAR

Today's date

Many people leak urine some of the time. We are trying to find out how many people leak urine, and how much this bothers them. We would be grateful if you could answer the following questions, thinking about how you have been, on average, over the PAST FOUR WEEKS.

1 Please write in your date of birth:

DAY MONTH YEAR

2 Are you (tick one):

Female Male

3 How often do you leak urine? (Tick one box)

- never 0
 about once a week or less often 1
 two or three times a week 2
 about once a day 3
 several times a day 4
 all the time 5

4 We would like to know how much urine you think leaks.

How much urine do you usually leak (whether you wear protection or not)?
 (Tick one box)

- none 0
 a small amount 2
 a moderate amount 4
 a large amount 6

5 Overall, how much does leaking urine interfere with your everyday life?

Please ring a number between 0 (not at all) and 10 (a great deal)

0 1 2 3 4 5 6 7 8 9 10
 not at all a great deal

ICIQ score: sum scores 3+4+5

6 When does urine leak? (Please tick all that apply to you)

- never – urine does not leak
 leaks before you can get to the toilet
 leaks when you cough or sneeze
 leaks when you are asleep
 leaks when you are physically active/exercising
 leaks when you have finished urinating and are dressed
 leaks for no obvious reason
 leaks all the time

Thank you very much for answering these questions.

Copyright © "ICIQ Group"

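### The single primary outcome, muscle strength, has two unranked instruments and up to eight readouts, with no rule for which decides H1 and no adjustment across them

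*Combined protocol and SAP*

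**What the plan says.** - **Hypothesis of the Study.** H1 reads "H1: Exercise training with one on one video conference method is more effective in increasing muscle strength in patients with urinary incontinence". It is directional and names no instrument, component or visit.
- **Evaluations, Table 1.** Muscle strength is the only primary outcome. Its evaluation methods are "PERFECT Scheme -Surface Electromyography", listed together without ranking.
- **Evaluations, timing.** "Evaluation parameters will be applied at the baseline, at the end of 4-weeks treatment program, at the end of 8 weeks treatment program". Neither post-baseline visit is named as deciding.
- **"Annex 3. Assessment of Muscle Strength".** The form has five PERFECT columns (power, endurance, repetitions, fast contractions, contraction time) and three surface-EMG columns (resting tone, maximum voluntary contraction or MVC, endurance). Each column has three trials and a mean. Trials are combined, but readouts are not, and there is no total score.
- **Statistical Analysis Plan.** "the significance will be evaluated at the $p < 0.05$ level", in a sentence that also mentions a 90% confidence interval. Baseline, week 4 and week 8 are compared by ANOVA. If normality fails, "comparisons will be made with Kruskal Wallis and appropriate post-hoc tests". No primary readout, decision rule or adjustment across readouts is given.

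The part of the document between the SAP and Annex 2 was not available for review. The sections where a decision rule would be expected (hypotheses, Table 1, SAP) were available, and the SAP section reads as complete.

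**The concern.** A primary outcome is meant to fix in advance the one result on which the main hypothesis stands or falls. Here the construct is fixed but the measurement is not. An analyst who follows the plan will test at least one variable from each instrument, each at 0.05, and nothing says how a mixed picture is to be read. If PERFECT power favours one-on-one and the EMG does not, the plan supports calling H1 confirmed and equally supports calling it unconfirmed.

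The choice could therefore be made after the data are seen, and a favourable readout reported as the primary result. A reader of the final report could not tell a pre-planned success from one selected among several.

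The SAP's reference to post-hoc tests does not close the gap. It names no method, and it is attached to follow-up comparisons after a Kruskal-Wallis test of a variable, not to the family of different variables that make up the primary outcome.

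**Working it through.** The text available gives no sample size, power or familywise error rate, so there is no figure of the plan's own to reproduce. The check asks how far the false-positive rate moves if the open choice is used.

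**Inputs from the documents**
- Instruments for the primary outcome: 2 (Table 1).
- Readouts on the form: 5 + 3 = 8 (Annex 3). The three trials per readout are averaged and do not enlarge the family.
- Significance level: 0.05 per test (SAP).

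**Assumptions, none in the documents**
- Any one readout suffices for H1.
- One between-group test per readout, at one visit.
- Two-sided tests, critical value 1.960, so 2.5% per direction.
- Equal correlation ρ between the test statistics, from 0 to 0.9.

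**Independent readouts (ρ = 0).** The chance of at least one false positive is 1 − (1 − α)^k.
- k = 2, either direction: 1 − 0.95² = 0.0975. Favouring one-on-one: 1 − 0.975² = 0.0494.
- k = 8, either direction: 1 − 0.95⁸ = 0.337. Favouring one-on-one: 1 − 0.975⁸ = 0.183.

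**Correlated readouts.** Write each statistic as Z_j = √ρ·C + √(1−ρ)·E_j, with C and E_j independent standard normal. Then

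P(any |Z_j| > 1.960) = 1 − ∫ [Φ((1.960 − √ρ·c)/√(1−ρ)) − Φ((−1.960 − √ρ·c)/√(1−ρ))]^k φ(c) dc.

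For results favouring one-on-one, the second Φ term is dropped. Numerical integration gives:

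| Readouts | Direction | Nominal | ρ = 0 | 0.5 | 0.7 | 0.9 |
|---|---|---|---|---|---|---|
| 2 | either | 5% | 9.8% | 9.1% | 8.3% | 7.0% |
| 2 | favouring one-on-one | 2.5% | 4.9% | 4.5% | 4.2% | 3.5% |
| 8 | either | 5% | 34% | 25% | 19% | 12% |
| 8 | favouring one-on-one | 2.5% | 18% | 13% | 10% | 6% |

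The plan does not say which direction is favourable for resting tone, so the last row is approximate.

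**Small-sample check.** With t tests and an assumed 16 per arm, two readouts give 9.6%, 8.8% and 7.1% in either direction at ρ = 0, 0.5 and 0.9. With 24 per arm they give 9.7%, 9.2% and 7.2%. The normal approximation is adequate.

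**The same two readouts under a stated rule**
- Either, with Holm: the first step is at 0.05/2 = 0.025 (critical value 2.241). The false-positive rate in either direction is 4.9% at ρ = 0 and 3.6% at ρ = 0.9.
- Both must pass at 0.05: the chance that both falsely favour one-on-one, with no effect on either, is 0.06% at ρ = 0 and 1.5% at ρ = 0.9. There is no inflation.

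**The case against.** The strongest reply is that the inflation is conditional. The plan never says that one favourable readout is enough. If both instruments must agree, the error rate is not raised at all, and what remains is ambiguity. That is right, and the percentages above should be read as the size of the exposure, not as the plan's error rate. It does not remove the point, because the plan does not require agreement either.

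Three stronger readings are tempting, and the documents do not support them.

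- **That the 5% level for H1 is broken even with two readouts.** H1 is directional, so a result favouring group sessions cannot support it. Under the stated assumptions the chance of falsely supporting H1 is 4.9% to 3.5%. That exceeds the 2.5% per-direction level but not 5%. Only the rate in either direction, 9.8% to 7.0%, exceeds 5%.
- **That the eight-readout figures are the expected error rate.** Annex 3 is a recording form, not an endpoint list. Resting tone, the two endurance columns, repetitions and contraction time are not strength in the narrow sense. The form's heading covers all eight and nothing limits the outcome to power or MVC, so the count is fair as an upper bound only. Two instruments is the reading the text supports most directly.
- **That weeks 4 and 8 double the number of tests.** The SAP describes one ANOVA over three time points, not separate between-group tests at each visit. The SAP does not say which effect or contrast tests H1, and the unnamed post-hoc tests leave room for choosing a visit, so further inflation is possible. The text gives no sound basis for quantifying it.

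**Conclusion.** The concern holds as a gap in pre-specification that should be closed. The only primary outcome has two unranked instruments, and the available text gives no deciding readout, visit, composite, any/all rule or adjustment.

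On the best-supported reading (one readout per instrument, one visit), and if either may suffice, the false-positive rate is up to about twice nominal in both framings. It remains above nominal even at a correlation of 0.9. The eight-column figures bound the problem from above.

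The result rests on the any-one-suffices assumption, two-sided tests at 0.05 and the assumed correlation range. The nominal level is itself unclear, because the SAP pairs p < 0.05 with a 90% confidence interval and does not state sidedness. It would be wrong to infer that the plan intends to pick the best readout. The documents show only that it does not prevent this.

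**What to change.** Before outcome data are examined, amend Table 1 and the SAP as follows.

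1. Name one primary readout that is already collected, for example surface-EMG MVC or PERFECT power, as the between-group comparison at week 8. The choice between them belongs to the investigators.
2. If both instruments are kept, name one readout from each and state the rule: either may support H1 with Holm adjustment, or both must pass at 0.05.
3. List the remaining PERFECT and EMG readouts, and the week-4 results, as secondary or exploratory.
4. State the sidedness of the test and bring the confidence level into line with the significance level.

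**Cost.** No new data are needed. Other readouts can no longer be claimed as primary successes. A single named readout needs no adjustment and loses no power for that readout.

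Keeping two costs power, either per readout (Holm) or overall (both must pass). As an illustration, assume each readout has 80% power at 0.05; the available text states no power. For correlations from 0 to 0.9:
- Either with Holm gives about 92% to 77% power for at least one success. It needs more participants to keep 80% only at high correlation (about 6% more at 0.9).
- Both must pass gives about 64% to 75%, and needs about 31% to 12% more participants to restore 80%.
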